8.2 Patient recruitment

(i) Cohort study of clinical outcomes

Women will be provided with the study information leaflet as they register their attendance at the clinic reception. Once they have had sufficient time to read the information leaflet they will then be approached by the triage (registered) nurse or midwife/research nurse or midwife/nurse sonographer/trial officer/research team lead/clinical research fellow/doctor and asked to participate in the study. Women who agree to participate will sign a consent form at this point.

Demographic and routine clinical data will be collected from all women attending the EPAUs. In women who consent to the study their clinical data and questionnaires will be linked using their study number. The data from women who do not consent will be anonymised and the data collection forms will not leave individual hospital premises.

(ii) Health economic evaluation

Step 1. Women who consent to the study will be asked to complete the EuroQoI-5D 5L (EQ-5D 5L) questionnaire and the Visual Analog Anxiety Scale (VAS-A) prior to their clinical assessment. They will also be asked to complete the same VAS-A at the end of their visit. In case of follow-up visits, women who consented to participate in the study will be asked to complete the VAS-A prior to and following review.

Step 2. Women who consent to the study will also be asked to complete the EQ-5D 5L questionnaire two weeks after discharge from the clinic.

Step 3. A sub-set of women, across all sites and stratified by outcome, will be asked to complete the EQ-5D-5L as well as a more detailed questionnaire about service use - the Client Service Receipt Inventory (CSRI) - 12 weeks post-discharge.

(iii) Patient satisfaction survey

Women who consent to the study will be asked to complete the Short Assessment of Patient Satisfaction (SAPS) measure as well as a condition-specific patient satisfaction questionnaire (modified Newcastle-Farnworth questionnaire) at two weeks post-discharge. Further information about the pregnancy, including the London Measure of Unplanned Pregnancy (LMUP) will also be collected.

(vi) Qualitative interviews with service users

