9.1 Sample size calculation

We plan to recruit 44 units, each contributing at least 150 patients. This will give us 90% power to detect a difference in admission of rates of 5% (8.5% vs 3.5%) between units with a low consultant presence and those with a high presence, at the 5% significance level. The results from our pilot study suggest that such a difference in admission rates is both clinically relevant and likely.

This sample size calculation is based on a simplified analysis where units are classed as having either low or high consultant presence based on a dichotomisation at the median level of consultant presence. The admission rates for the patients in the 22 units with "high" consultant presence are then to be compared to those from units with "low" consultant presence. A basic sample size calculation (that assumes no clustering) suggests that we require 946 patients in total (or 22 per unit). However, assuming a moderate level of clustering (ICC = 0.04) we would require 150 patients per Unit. Data collection for each unit will be for minimum seven days to ensure weekday/weekend variation is captured.

For the subsidiary data strands, the anticipated response rates are as follows:

(ii) Health economic evaluation

In the absence of prior knowledge of the expected values and standard deviations of costs and effects (in this case, QALYs) it is not possible to formally estimate a required response rate. Therefore, we have taken a pragmatic approach to determining the number of resource use questionnaires to collect. Our aim is to balance the collection of sufficient data to make inferences about cost-effectiveness against the burden on women of being asked to complete data collection forms shortly after the loss of a pregnancy.

Questionnaires will be sent to randomly chosen women, selected from those who have given prior consent for further contact. The sample will be stratified using the same criteria as used to select participating EPAUs. We anticipate that 320 completed questionnaires will provide sufficient data.

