An algorithm and approach to sampling similar to that used to select units for participation in the study, will be used to select women to be approached to complete the resource use questionnaire. The key factors used to sample will be consultant presence (at four levels), weekend availability and number of patients attending. Each stratum of each key factor will be equally represented. That is, 80 women will be in stratum 1 for consultant presence, 80 will be in stratum 2, and so on. Likewise, 160 women will be in stratum 1 for weekend opening and 160 will be in stratum 2, and similarly for number of patients attending a unit. Women will be approached to complete the resource use questionnaire until we achieve 320

responses balanced across factors and strata.

In order to accurately capture the workforce resources needed to run each EPAU, we will prospectively collect data on members and grades of staff involved in providing care as well as the time spent providing this care. Consultant presence will be collected prospectively for each session/day that data will be collected for (i.e. a record of whether a consultant is physically present in the unit reviewing patients will be collected for every session for which we are collecting data).

(iii) Patient satisfaction survey

Our study population will include 6600 women (150 x 44 units, see above). If our response rate is 30%, then a 95% confidence interval (for a yes/no question) will have a margin of error of at most 2.2%. If the response rate is just 10%, then the error will be at most 3.8%.

(iv) Staff survey

We expect that there will be approximately 200 staff members in the sample of 44 units. If our response rate is 50%, then a 95% confidence interval (for a yes/no question) will have a margin of error of at most 10%.

(v) Qualitative interviews with service users

Forty interviews will be carried out with EPAU service users. This calculation is based on the needs of the intended maximum variation sample^{18,19} (enabling representation by region, pregnancy outcome, and reported level of satisfaction) and will provide a wealth of qualitative data for analysis.

(vii) Hospital emergency care audit

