9.3.2 Secondary outcome analysis

The analyses of the secondary outcomes (number of follow-up visits, non-diagnostic ultrasound scans, negative laparoscopies, estimated blood loss at surgery and ruptured ectopic pregnancies requiring a blood transfusion, patient satisfaction) will follow a similar pattern although the type of regression model will be tailored for the specific outcome measure (e.g. hierarchical Poisson/linear regression will be used to analyse number of follow-up visits). Regression modelling will also be used to analyse the effect of opening hours and service accessibility on the overall admission rates and other clinical outcomes. Again, the type of regression model will depend on the clinical outcome and opening hours / service accessibility will be treated as exposure variables.

Health Economic analysis

The economic evaluation will comprise two parts:

- a within-study analysis, and
- a longer-term, model based, analysis.

The within-study analysis will focus on the costs and outcomes during the study period and will be based on the data collected during the study. The longer-term model based analysis will supplement the study data with data from the literature, particularly on patient outcomes. These additional data will be used to estimate the cost-effectiveness of different staffing configurations when longer term outcomes are taken into consideration.

In each analysis we will examine the cost-utility of different skill-mix configurations for staffing EPAUs. Outcomes for each analysis will be 1) patient quality of life, measured as quality adjusted life years (QALYs) and 2) admissions avoided.

Costs will be estimated from a societal perspective (capturing costs to the NHS, social services and patients). Results will be reported as the incremental net benefit of the modelled skill-mix configurations, and incremental cost-effectiveness ratios.

Uncertainty will be captured in the analyses through probabilistic sensitivity analysis and reported using cost-effectiveness acceptability curves, showing the likelihood a particular skill-mix model will be cost-effective over a range of values of the societal willingness to pay for a QALY.

In this section, we detail how we will collect and analyse data for the economic evaluation and how this will link with the skill-mix modelling.

Skill-mix model development:

The services delivered by a given EPAU are determined by two broad factors:

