Using the skill-mix model analysis we will then evaluate the cost utility of the set of identified potentially optimal skill-mix configurations. This analysis will combine the results of the skill-mix modelling configurations (with associated costs), patient outcome data, patient resource use data and data on additional costs to patients, social services and the NHS not already captured in the EPAU unit configuration costs. Results of the economic evaluation will be reported in standard metrics, including:

- The incremental cost-effectiveness ratio (ICER) of an additional admission avoided, (cost per additional avoided)
- The ICER based on quality adjusted life years (cost per QALY gained), and
- the net benefit statistic.

Sensitivity analysis will be used to test assumptions about the model structure, to explore the generalizability of the results and to capture the underlying uncertainty in the sample data. Probabilistic sensitivity analysis will be used to capture the uncertainty arising from the sampled data, with model parameters defined as probability distributions and Monte Carlo simulations used to simulate repeated trials. Structural uncertainty in the model (for example, relating to variability in individual skill-mix configurations or local staff availability) will be explored using one-way and scenario analyses. Additional one and two-way analyses will be used to explore further the generalisability of the results.

Primary within-study analysis

The primary economic evaluation will be a within-study analysis. As described above, in the analysis we will estimate incremental cost-effectiveness ratios for the two main outcomes of interest, patient quality of life (in QALYs) and admission rates. These will be reported together with associated Bayesian credible intervals, based on the data collected in during

the study period. For this analysis data will be drawn as far as possible from the study data. Monte Carlo simulation methods will be used to construct a cost-effectiveness acceptability curve, based on the expected net benefit statistic, to estimate the probability that the intervention is cost-effective for a range of values of societal willingness to pay per QALY. We will also subject the results to extensive deterministic (one, two, and multi-way) sensitivity analysis.

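### Credible intervals are planned on the cost-effectiveness ratios themselves, with no rule for a QALY difference that may be zero or negative

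*Protocol*

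**What the plan says.** Protocol section 9.3.2, under the primary within-study analysis, states that "we will estimate incremental cost-effectiveness ratios for the two main outcomes of interest", these being QALYs and admission rates. The next sentence begins "These will be reported together with associated Bayesian credible intervals". The natural antecedent is the ratios, so the intervals are intended for the ICERs. Nothing in the section says what happens when the effect difference is close to zero or changes sign.

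The same section also plans other measures. Its Health Economic analysis overview says "Results will be reported as the incremental net benefit of the modelled skill-mix configurations, and incremental cost-effectiveness ratios". The paragraph that contains the interval sentence adds: "Monte Carlo simulation methods will be used to construct a cost-effectiveness acceptability curve, based on the expected net benefit statistic".

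On precision, section 9.1 sets no target for the economic strand. It begins "In the absence of prior knowledge of the expected values and standard deviations of costs and effects" and settles on a pragmatic number: "We anticipate that 320 completed questionnaires will provide sufficient data". Those responses are balanced over four levels of consultant presence, so that "80 women will be in stratum 1 for consultant presence" and likewise for the other three. Section 8.2 places the detailed resource-use questionnaire and a further EQ-5D-5L in a sub-set ("CSRI) - 12 weeks post-discharge"). It asks all consenting women for EQ-5D-5L on arrival and again two weeks after discharge.

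**The concern.** An ICER is a cost difference divided by an effect difference. If posterior draws of the effect difference lie on both sides of zero, the ratio runs off to plus and minus infinity around that point, and its sign no longer tells good from bad. A negative value may come from a configuration that is cheaper and better, or from one that is dearer and worse. A positive value may mean paying more for a gain (north-east) or saving money at the price of a loss (south-west), and these are judged in opposite directions against a threshold. Sorting such draws and taking the 2.5th and 97.5th percentiles does not order configurations from favourable to unfavourable.

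At stake is the error bar beside the cost per QALY in what the protocol calls its primary economic evaluation. Because section 9.1 declares the expected effects and their spread unknown, the plan has no basis for assuming that the denominator will stay clear of zero.

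**Working it through.** The protocol states no figure for the ICER or its interval. Its only reproducible figures here are those for the primary outcome, which also give the standard error for the admissions denominator.

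**1. The plan's own figures.** Inputs from section 9.1: 8.5% v 3.5%, 90% power, 5% significance (taken as two-sided), ICC 0.04, 44 units of 150. Two proportions with pooled variance and no continuity correction give 473 per group, or 946 in total, as stated. The design effect is 1 + 149 x 0.04 = 6.96, and 946 x 6.96 = 6,584 against 6,600 planned. The figures reproduce.

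**2. Admissions denominator.** With 90% power for 5 points, SE = 5 / (1.96 + 1.28) = 5 / 3.24 = 1.54 points. The share of draws below zero is Phi(-difference / SE):

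| True difference (points) | Draws below zero |
|---|---|
| 5 (planned) | 0.06% |
| 3 | 2.6% |
| 2 | 10% |
| 1 | 26% |

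**3. QALY denominator if it rests on the 320-woman subset.** Assumed, not in the documents: utility SD 0.15-0.25, sustained utility difference 0.02, no clustering, and a two-group contrast of 80 v 80 or 160 v 160. Over 12 weeks the QALY difference is 0.02 x 12/52 = 0.0046. SE(utility) = SD x sqrt(2/n). The 12/52 factor cancels in the share below zero, which is Phi(-0.02 / SE).
- 160 v 160, SD 0.15: SE = 0.0168, share 12%.
- 80 v 80, SD 0.15: SE = 0.0237, share 20%.
- 80 v 80, SD 0.25: SE = 0.0395, share 31%.

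Holding the share under 2.5% needs a difference of 1.96 x SE, which is 0.033 (160 v 160, SD 0.15) to 0.077 (80 v 80, SD 0.25).

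**4. QALY denominator if it rests on two-week EQ-5D.** Section 9.1 uses 30% as an illustrative response rate for the satisfaction survey. Applied here, 0.30 x 6,600 = 1,980, or 990 v 990, with 45 per unit. Assumed SD 0.20 and difference 0.02.
- No clustering: SE = 0.20 x sqrt(2/990) = 0.0090, share 1.3%.
- ICC 0.04: design effect 1 + 44 x 0.04 = 2.76, SE = 0.0149, share 9%.

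**5. How a percentile interval for the ratio behaves.** Illustration at 80 v 80 with the difference from step 3, plus an assumed cost difference of 100 pounds, cost SD 1,000, independence of costs and effects, and raw percentiles of the ratio. The true ICER is 100 / 0.0046, about 21,700 per QALY. SE(cost) = 1,000 x sqrt(2/80) = 158, so 26% of cost draws are negative. With SD 0.15, 20% of effect draws are negative, and the quadrant shares are: dominant 0.26 x 0.80 = 21%, dominated 0.74 x 0.20 = 15%, south-west 0.26 x 0.20 = 5%, and north-east the remaining 59%.

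Net benefit is taken at an assumed 20,000 per QALY. Its SE is sqrt((20,000 x SE of QALY difference)^2 + 158^2), which is 192 at SD 0.15 and 241 at SD 0.25, around a mean of 20,000 x 0.0046 - 100 = about -8.

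| Utility SD | 95% interval for ICER (simulated) | 95% interval for net benefit |
|---|---|---|
| 0.15 | about -290,000 to +320,000 | -385 to +369 |
| 0.25 | about -226,000 to +236,000 | -481 to +465 |

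As the data become noisier, the ICER interval narrows while the net-benefit interval widens as it should. In this setting the width of the ICER interval does not measure information.

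**The case against.** A reader might infer that the QALY difference will very likely straddle zero. The documents do not support that. They give no expected difference or SD, so every percentage in steps 3 to 5 rests on supplied inputs. At a utility difference of 0.05, the 95% interval for the QALY difference would include zero with probability 15-57% at 160 v 160 (SD 0.15-0.25), and only 0-8% at 990 v 990 (SD 0.20, ICC 0 to 0.04). The 12-week horizon and the 80 or 160 per group also belong to the resource-use subset. Section 9.3.2 ties the 3-month follow-up sub-sample to the secondary modelling analysis, and the groups to be compared are skill-mix configurations identified later, not consultant-presence strata. This objection stands, which is why both bases are shown and neither is offered as the expected result.

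A reader might also infer that both ICERs would carry meaningless intervals. For admissions that fails at the planned 5 points, where about 0.06% of draws fall below zero.

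Net benefit and acceptability curves are already planned, in the same paragraph among other places, and they carry the decision uncertainty properly. That stands and lowers the severity. It does not make the ratio interval valid, and the interval would still be reported.

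Finally, the protocol does not say that raw percentiles will be used, and section 12 leaves detail to an analysis plan agreed before analysis. The construction can indeed be settled there. But the protocol has already committed to intervals on the ratios without any condition, and no choice of percentiles restores a single meaning once the denominator's posterior spans zero.

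**Conclusion.** The plan is wrong as written on a narrow point, and the severity is minor. It commits to credible intervals on the ICERs unconditionally, and such an interval cannot be interpreted if the posterior for the QALY difference spans zero. That is plausible but not established. At an assumed utility difference of 0.02, about 12-31% of draws fall below zero on the 320-woman subset (SD 0.15-0.25, no clustering), and about 1-9% on two-week EQ-5D at 30% response (SD 0.20, ICC 0 to 0.04). The problem recedes with larger differences, smaller SDs or larger samples. The admissions ICER is affected only if the true difference is about 3 points or less, using the planning SE for the full cohort. It would be too strong to conclude that the economic evaluation lacks a valid measure of uncertainty, since the planned net benefit and acceptability curves supply one.

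**What to change.** Replace the interval sentence in the primary within-study analysis of section 9.3.2 so that credible intervals are given for incremental cost, incremental QALYs, admissions avoided, and incremental net benefit at stated thresholds. Report each ICER as a point estimate with the share of posterior draws in each quadrant of the cost-effectiveness plane. Add an interval for an ICER only when the posterior of its denominator stays clear of zero, and fix that criterion in advance, for example that the 95% credible interval for the effect difference excludes zero. This keeps a usable interval for cost per admission avoided if the planned effect is real.

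The cost is a few lines of wording. The same Monte Carlo draws supply every quantity, and no data collection or sample size changes.

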5 STUDY SCHEDULE

5.1 Randomisation procedure

The process for selecting the Units is described in section 8.1. There will be no randomisation of individual patients.

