9.3 Statistical analysis plan

9.3.1 Primary outcome analysis – Cohort study of clinical outcomes

The primary analysis will investigate whether consultant presence is associated with admission rate. We will perform a patient-level analysis and hence will use hierarchical logistic regression models that allow for patient clustering within EPAUs. Consultant

presence will be modelled as a continuous variable. The use of regression modelling will allow us to adjust for confounding factors, which may be associated with higher admission rates. The results of this analysis will be reported in terms of odds ratios (with corresponding confidence intervals and P-values) to indicate the degree of association. All model assumptions will be checked. Specifically, level 2 residuals will be checked for normality and linearity assumptions will be checked. The ICC, which indicates the degree of clustering within EPAUs, will also be reported. Multiple imputation will be used if there is a high degree of missing data.

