- 1. the workforce delivering the required care, and
- 2. the clinical approach used to deliver that care (for example the thresholds for certain tests to be offered may be different even in configurations where the staff make-up is similar).

Using the clinical and operational data collected as part of the cohort study of clinical outcomes, we will identify skill-mix models appropriate for further consideration in a costutility analysis. This first stage of analysis will define appropriate EPAU skill-mix configurations for assessment in cost-utility analysis. The set of alternative staffing configurations will be used to estimate the expected costs of different skill-mix models, based on what is already known about the studied EPAUs. These models will consider both skill-mix and other factors that determine the cost of delivery local services.

The costs for each EPAU to deliver services will also vary according to each configuration as these will be dependent on the make-up of the local workforce as well as the local costs of

premises and equipment. While care pathways may be consistent across the country as a result of the nationally adopted guidelines, the scale and size of each EPAU will be different due to the service requirement of each locality due to population size, epidemiological factors and local socio-economic characteristics (such as ethnicity, levels of deprivation and education). This means that the workforce size and EPAU cost required to meet the service requirement will be locally dependent, and we will account for variation in costs in the analysis.

Within the skill-mix model we will consider the level of consultant presence, as well as the number and grade of other clinical and support staff available. The costs of implementing any configuration will include both the quantity of each skill set (consultant, junior doctor, nurse etc) required and the coverage time for which they are required. Another important factor to consider in skill-mix models will be case mix. A complex case mix may create a workload equivalent to that in a bigger unit with a less complex or complicated case mix.

Development of optimal skill mix model to run

Cost-utility analysis overview:

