The analysis process will be as follows: Initial data exploration will be conducted using standard frequentist statistical approaches. First we will compare baseline costs and other factors between groups to determine if any of the baseline characteristics predict costs. Where there are differences appropriate methods will be used to standardise/adjust for these. Unadjusted costs and outcomes will be estimated and reported. Regression analyses will be used to adjust for differences in baseline characteristics and adjusted values will also be reported. Estimates of skewness will be calculated for all resource use variables. As resource use data are commonly skewed, appropriate regression methods will be required (eg GLM) to account for this.

We will explore whether there are baseline characteristics across each group that explain differences in costs. This will be used to explain how costs are linked to baseline characteristics and the intervention. This will help us understand skill-mix variation effects holding everything else constant. It can also help us understand what the drivers of patient costs are and whether they are associated with any between group differences. Coefficients and p-values will be reported for each model tested.

Once we have explored the data and assessed for any important difference in baseline characteristics cost-effectiveness analysis can be undertaken. Unadjusted data will be used for the cost-effectiveness analysis. Simulation methods as described by O'Hagan and others²² will be applied. As is common with healthcare data, costs are expected to be skewed due to a small number of patients who typically consume a disproportionately large level of resources. As a result, the assumptions required for standard statistical approaches based on normally distributed data do not hold. A Bayesian parametric approach to analysis of costs will be followed to address concerns arising from the expected non-normality of the data.

Changes in reported anxiety measured using the visual analog scale will also be evaluated. Anxiety measures will be taken at the baseline data collection point, at the end of the initial visit to the EPAU prior to discharge and then at any clinic follow-up appointments. In the absence of an accepted minimally important difference in anxiety scores a standardised scoring based on Cohen effect sizes will be applied, with 0.2 assumed to be 'small' effect size, 0.5 medium effect size and 0.8 a large effect.

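### The primary cost-effectiveness analysis is fixed on unadjusted data in a non-randomised comparison between units, against the protocol's own adjustment plan

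*Protocol*

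**What the plan says.** Protocol section 9.3.2, under Primary within-study analysis, gives the analysis its status: "The primary economic evaluation will be a within-study analysis". It is to produce ICERs for QALYs and for admissions, with Bayesian credible intervals and an acceptability curve built on expected net benefit.

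The steps follow in this order:

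- Baseline costs and other factors are compared between groups. "Where there are differences appropriate methods will be used to standardise/adjust for these".
- Unadjusted costs and outcomes are reported. Then: "Regression analyses will be used to adjust for differences in baseline characteristics and adjusted values will also be reported".
- "Once we have explored the data and assessed for any important difference in baseline characteristics cost-effectiveness analysis can be undertaken". The next sentence reads: "Unadjusted data will be used for the cost-effectiveness analysis".

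Three other places bear on this:

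- Section 5.1: "There will be no randomisation of individual patients". Section 15 classes the study as observational.
- Section 9.3.2, Skill-mix model development, says that unit size and cost depend on population, epidemiology and local socio-economic features such as ethnicity, deprivation and education. On workload it says: "A complex case mix may create a workload equivalent to that in a bigger unit with a less complex or complicated case mix".
- Section 9.3.1 analyses admissions with "hierarchical logistic regression models that allow for patient clustering within EPAUs" and adjusts for confounders.

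**The concern.** In a randomised comparison, unadjusted costs and effects would be a defensible base case. Here the groups are defined by how each unit is staffed, and units with different staffing may serve different women. An unadjusted difference in cost, QALYs or admissions then mixes the effect of skill mix with differences in case mix, locality and starting quality of life.

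The plan looks for those differences, says it will adjust for them, and then assigns the decision analysis to the unadjusted data. No text takes the adjusted values into the ICER, net benefit or acceptability curve.

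The cost-effectiveness of skill-mix models is a stated secondary objective (section 3.2), and the same list ends with recommendations on how UK units should be configured. One quantity, admissions avoided, would also have two estimates: an adjusted one in the clinical analysis and an unadjusted one as an ICER denominator. These could disagree, and the protocol does not say which would prevail.

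**Working it through.** **1. The statements side by side**

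| Element | Clinical analysis (9.3.1) | Within-study economic analysis (9.3.2) |
|---|---|---|
| Randomised? | No | No |
| Confounding | Adjusted by regression | Adjusted values reported; cost-effectiveness analysis on unadjusted data |
| Admissions | Adjusted | Unadjusted in the ICER |
| Clustering within units | Hierarchical model | Not mentioned, neither included nor excluded |

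The third row follows directly from the second. The contradiction is in the text and needs no arithmetic.

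**2. Can the confounding be sized?**

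No. The document gives no baseline EQ-5D-5L values, no cost figures and no case-mix distribution by staffing level. An illustration shows how far any number depends on assumptions. Suppose a baseline EQ-5D gap of 0.03 to 0.05 (assumed) is carried forward unchanged:

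- over 12 weeks: 0.03 × 12/52 = 0.007 and 0.05 × 12/52 = 0.012 QALYs;
- over 2 weeks, the first post-discharge EQ-5D-5L: 0.03 × 2/52 = 0.001 and 0.05 × 2/52 = 0.002 QALYs.

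The within-study analysis is tied only to the study period, and the 26-week/3-month data are assigned to the secondary model. Neither the gap nor the horizon is fixed by the document.

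**3. Clustering: what would be at stake if it were left out**

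The plan's own figures come first (section 9.1: 8.5% vs 3.5%, 90% power, 5% level taken as two-sided, 44 units, ICC 0.04 for admissions).

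- Unclustered size per group, pooled variance: [1.96 × √(2 × 0.06 × 0.94) + 1.2816 × √(0.085 × 0.915 + 0.035 × 0.965)]² / 0.05² ≈ 472.0, rounded up to 473. The total is 946, as stated, or 946/44 = 21.5 per unit.
- Women per unit m solving m / [1 + (m − 1) × 0.04] = 21.5: m = 21.5 × 0.96 / (1 − 21.5 × 0.04) = 147.4, consistent with the stated 150.
- At 150 per unit, effective N = 6600/6.96 = 948, and power is 90.1%.

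The exposure belongs to the unit, so the full design effect applies. With DE = 1 + (m − 1) × ICC, a standard error that ignores clustering is too small by √DE:

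| Data source | m per unit | DE at ICC 0.04 | √DE | Coverage of a nominal 95% interval | √DE for ICC 0.01 to 0.10 (assumed range) |
|---|---|---|---|---|---|
| Admissions, all women | 150 | 6.96 | 2.64 | 54% | 1.58 to 3.99 |
| Resource-use sub-sample | 320/44 = 7.27 | 1.25 | 1.12 | 92% | 1.03 to 1.28 |

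The ICC of 0.04 is stated for admissions only. The second row borrows it and assumes that the 320 responses are spread evenly over the 44 units. No ICC is given for costs or QALYs.

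**The case against.** The other side has several fair points.

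- **Adjusted values will be reported.** True, but as additional output. Nothing routes them into the ICER, net benefit or acceptability curve.
- **The protocol says it will account for local variation in costs, and it names case mix in the skill-mix models.** The cost statement concerns what it costs a unit to deliver its service, gives no method, and does not reach QALYs or admissions. Naming case mix as a factor does not override the explicit rule on unadjusted data.
- **The 320 responses are balanced.** They are balanced on consultant presence, weekend opening and attendance volume (section 9.1), but not on case mix, deprivation or baseline EQ-5D-5L. The balancing also does not apply to admissions or to the two-week EQ-5D-5L in all consenting women.
- **Extensive sensitivity analyses are planned.** As described, they address model structure, generalisability and parameter uncertainty. None is stated to deal with confounding.
- **Details belong in the analysis plan.** This is right for matters on which the protocol is silent. The use of unadjusted data is a stated rule, so an analysis plan could adjust only by departing from the protocol.

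The last point does stand for clustering. A reader might infer that the economic analysis ignores clustering and that its intervals will be too narrow. The document does not support that. It specifies a Bayesian parametric approach because costs are skewed, and says nothing either way about a unit effect. Section 12 foresees a detailed analysis plan, which could contain one.

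**Conclusion.** The point holds in this form: the protocol fixes its primary economic comparison, which is not randomised and is made between units, on unadjusted data. That contradicts its own statement on adjustment and leaves admissions avoided handled differently in the economic and clinical analyses. The ICERs, net benefit and acceptability curve are exposed to confounding.

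A reader might go further and say that the results will be biased by a given amount. The document does not allow it: size and direction cannot be derived, and any QALY figure rests on an assumed EQ-5D gap and an assumed horizon.

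On clustering, the finding is a conditional one. If the unit effect were left out, the standard error for admissions would be about 2.6 times too small at 150 women per unit under the protocol's own ICC. It would be only about 1.1 times too small in the 320-woman sub-sample if that ICC carried over.

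The primary clinical hypothesis is unaffected, because its analysis is already adjusted and hierarchical.

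**What to change.** Replace the sentence on unadjusted data with wording such as:

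> *The primary ICERs, net benefit and acceptability curve will use costs, QALYs and admissions adjusted for case mix, unit-level confounders and, where recorded, baseline EQ-5D-5L. The models will include a unit-level effect, as in section 9.3.1. Unadjusted results will be presented as a sensitivity analysis.*

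This removes the contradiction within section 9.3.2 and brings admissions avoided into line with the clinical analysis. The form of the model can be left to the analysis plan; more than one hierarchical approach would serve. The analysis plan should also state the horizon of the within-study analysis and list the adjustment variables before the data are seen.

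The change relies on data already planned (section 8.2): demographic and routine clinical data on all women, and EQ-5D-5L on arrival in those who consent. The protocol does not list the case report form items, so the variable list must be limited to what is actually recorded. With 44 units, only a modest number of unit-level covariates can be supported. The cost is a wording amendment, somewhat more modelling work, and probably wider intervals.
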